5.5 Adverse Events Associated with Dental Disease

Incidences of subjects reporting adverse events associated with dental disease, per sponsor-provided list, will be reported for each treatment session.

Table B – Listing of Dental Disease Terms used for Analysis

Term		
Angular cheilitis	Breath odour	Bruxism
Candida infection	Chapped lips	Dental caries
Dental leakage	Dental necrosis	Device failure
Gingival bleeding	Gingivitis	Glossitis
Glossodynia	Haemoptysis	Lip swelling
Mouth cyst	Mouth swelling	Mucosal inflammation
Mucosal ulceration	Oral candidiasis	Oral discomfort
Oral pain	Periodontitis	Pulpitis dental
Sensitivity of teeth	Stomatitis	Swollen tongue
Tongue coated	Tongue discolouration	Tongue dry
Tooth abscess	Tooth fracture	Tooth infection
Tooth injury	Tooth loss	Toothache

Details of AEs associated with dental disease will be listed for each subject.

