9 STUDY ENDPOINTS

9.1 Safety Endpoints

- Occurrence, seriousness, severity, and causality assessment of adverse events at each study visit;
- Occurrence of adverse events of special interest (i.e., aspiration, aspiration pneumonia, choking, dysphagia) at each study visit as assessed by the Investigator;
- Columbia Suicide Severity Scale (C-SSRS) at each study visit; and
- Occurrence of dental adverse events.

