16.2.3 Dental Adverse Events

Dental and oral health will be followed closely throughout the course of the study, with exams performed by either a licensed dentist (DDS or DMD) at each site, or oral examination by the Investigator. Dental adverse events (i.e., anything related to oral and dental health) will be reported as such if:

- Any finding from the dental or oral exam is determined to be clinically significant or require treatment/follow-up with a dentist, in the opinion of the Investigator or study dentist.
- An issue related to tooth or mouth discomfort is mentioned by the subject in response to a traditional non-leading question (e.g., “how have you been feeling since the last time I saw you?”).

All adverse events meeting the classification of “dental adverse events” will be included in the all adverse events analysis, as well as designated as a dental adverse event in the adverse event eCRF to enable appropriate safety sub-analyses.

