2.6.2 Safety measures

Adverse events are recorded at each study visit, starting from the first injection of MYOBLOC on Day 1 of Treatment Session 1 and ending at study completion (i.e., 52 ± 1 week). Subjects who discontinue because of an adverse event before study completion will be contacted 13 weeks (±3 days) after their last injection of study drug to assess the adverse event. Serious adverse events, adverse events of special interest, and other immediately reportable adverse events were collected during the study period (or within 13 weeks ±3 days of last study drug injection for subjects discontinuing participation prematurely). Dental and oral health are followed closely throughout the course of the study by monitoring dental adverse events (DAE), as defined in the study protocol.

Vital signs (blood pressure, pulse, respiratory rate, and temperature) are measured after sitting quietly for at least 5 minutes at screening and each study visit, if applicable, at early termination from the study.

Subjects' suicidal ideation and behavior are measured at each study visit (including Day 1 and Weeks 4, 8, 13, 17, 26, 30, 39, 43, and 52) or, if applicable, early termination from the study, using the Columbia Suicidal Severity Rating Scale (C-SSRS). The C-SSRS baseline version (Appendix I of the protocol) will be used for Day 1, whereas the C-SSRS since last visit version (Appendix J of the protocol) will be used for all of the other visits. The C-SSRS has three subscales: suicidal ideation (Categories 1-5), suicidal behavior (Categories 6-10), and intensity of suicidal ideation. Both suicidal ideation subscale and suicidal behavior subscale have 5 yes-no categories each, with a sum score ranging from 0 to 5 and higher score indicating greater severity.

Category 1 – Wish to be Dead

Category 2 – Non-specific Active Suicidal Thoughts

Category 3 – Active Suicidal Ideation with Any Methods (Not Plan) without Intent to Act

Category 4 – Active Suicidal Ideation with Some Intent to Act, without Specific Plan

Category 5 – Active Suicidal Ideation with Specific Plan and Intent

- Category 6 – Actual Attempt
- Category 7 – Interrupted Attempt
- Category 8 – Aborted Attempt
- Category 9 – Preparatory Acts or Behavior
- Category 10 – Suicidal Behavior

The intensity of suicidal ideation has 5 items (2 are scored from 1 through 5 and the other three from 0 to 5), with a sum score ranging from 2 to 25 where higher score indicate greater risk.

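### The SAP's only described dental incidence summary picks events from a 36-term list, while the protocol identifies dental adverse events by an event-level eCRF designation; the two are not reconciled

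*SAP*

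**What the plan says.** Protocol 9.1 names four safety endpoints. One is "Occurrence of dental adverse events".

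Protocol 16.2.3 says what counts. Its opening is broad: "Dental adverse events (i.e., anything related to oral and dental health) will be reported as such if" one of two criteria is met. The first is an examination result, as judged by either the study dentist or the investigator: "Any finding from the dental or oral exam is determined to be clinically significant or require treatment/follow-up with a dentist". The second is a subject report: "An issue related to tooth or mouth discomfort is mentioned by the subject in response to a traditional non-leading question". The section also says how these events are to be found at analysis. Each goes into the analysis of all adverse events and is also "designated as a dental adverse event in the adverse event eCRF to enable appropriate safety sub-analyses".

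SAP 2.6.2 keeps that definition by reference, describing dental follow-up as "monitoring dental adverse events (DAE), as defined in the study protocol". SAP 2.9.2 says dental adverse events will be analysed by session, but not how one is recognised in the data. SAP 5.5 then gives the summary: "Incidences of subjects reporting adverse events associated with dental disease, per sponsor-provided list, will be reported for each treatment session". The terms follow in the Table B printed in that section (the SAP also labels a schedule table B).

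**The concern.** The protocol's case definition is a judgement about each event, recorded at the site. The SAP's is a property of the coded term. A term list cannot reproduce an event-level judgement: the same preferred term may be a dental adverse event in one subject and not in another.

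Safety is the primary objective, and this is one of its four named endpoints. If the dental table is built only from the list, the reported proportion of subjects with a dental adverse event answers a question other than the one the protocol poses. A reader of the report could not tell by how much.

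**Working it through.** The documents give no dental event rate, so there is no figure to reproduce. The check compares the texts, counts the list and adds an illustration based only on assumptions.

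**1. Is Section 5.5 the dental adverse event analysis?** SAP 2.9.2 names four event groups for analysis by session: treatment-emergent events, events of special interest, dental adverse events, and events of distant toxin spread. SAP 5.3 to 5.6 follow the same order: adverse events, special interest, dental disease, distant spread. Section 5.5 sits where the dental analysis belongs, and no other part of Section 5 describes a dental incidence summary.

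**2. Case definitions side by side.**

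| | Protocol 16.2.3 | SAP 5.5 |
|---|---|---|
| Unit of decision | The individual event | The coded term |
| Who decides | Investigator or study dentist, or subject report | Sponsor's list |
| Data field | Dental designation on the adverse event eCRF | Match to a Table B term |
| Link to the other | None stated | None stated |

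**3. The list.** Table B of Section 5.5 has 36 distinct terms. Table C of Section 5.6 (distant spread) has 50. No term is in both.

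- *Possible misses:* a designated event coded outside the 36. *Dry mouth*, for example, is in Table C and not in Table B, while *Tongue dry* is in Table B. A dry mouth event that met a 16.2.3 criterion would be designated but not counted in 5.5.
- *Possible additions:* an undesignated event coded to a listed term. *Haemoptysis*, *Device failure*, *Candida infection* and *Mucosal inflammation* are not oral or dental by their wording alone.

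**4. Illustration (all rates assumed).** Let *p* be the proportion of subjects with a designated dental event, *s* the share of those subjects the list captures, and *f* the share of the remaining subjects who have a listed but undesignated event. List-based incidence is

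*q* = *p·s* + (1 − *p*)·*f*

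Take N = 187 (the figure in SAP 2.5), *s* from 0.6 to 1.0 and *f* from 0 to 0.05:

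| *p* | Lowest *q* (*s* = 0.6, *f* = 0) | Highest *q* (*s* = 1, *f* = 0.05) |
|---|---|---|
| 5% (9.3 subjects) | 0.05 × 0.6 = 3.0% (5.6) | 0.05 + 0.95 × 0.05 = 9.8% (18.2) |
| 10% (18.7) | 0.10 × 0.6 = 6.0% (11.2) | 0.10 + 0.90 × 0.05 = 14.5% (27.1) |
| 20% (37.4) | 0.20 × 0.6 = 12.0% (22.4) | 0.20 + 0.80 × 0.05 = 24.0% (44.9) |

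The list-based figure can lie below or above the designated one. Equal totals would not show agreement either. With *p* = 20%, *s* = 0.8 and *f* = 0.05, *q* = 0.16 + 0.04 = 20%, yet 0.20 × 0.2 = 4% of subjects are missed and 0.80 × 0.05 = 4% are added, about 7.5 subjects each way (0.04 × 187). Only a cross-tabulation would reveal this.

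**The case against.** The strongest reply is that the SAP never gives up the protocol definition. Sections 2.6.2 and 2.9.2 refer to dental adverse events throughout, and 2.9.2 adds that they are included in the adverse event analysis. Section 5.5 has a different title, about dental disease, and does not use the abbreviation DAE. The table and listing shells are not in the available text, so a table based on the designation cannot be ruled out. Protocol 17.7 prescribes no dental incidence table that 5.5 could contradict; it asks only for a listing of abnormal dental findings. The study has a single arm and no hypothesis on this endpoint, and every treatment-emergent event is tabulated by preferred term and listed by subject, so no event disappears from the report.

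Much of this stands, and it limits the point. It does not remove it. No text describes a designation-based table, and the order of topics in 2.9.2 points to 5.5 as the place where the dental analysis is carried out. The all-event tables do not give the proportion of subjects with at least one dental adverse event.

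Three stronger readings are tempting, and the documents support none of them:

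- *That dental events are in fact lost or wrongly added.* The origin of the list is not stated. If it was compiled from the terms of all designated events, nothing designated would be missed (*s* = 1). Undesignated events sharing a term could still be added, but whether any exist is unknown.
- *That dry mouth was wrongly left out.* Protocol 16.6 makes persistent dry mouth an example of a reason for an extra dental examination; it does not call it a dental adverse event. It qualifies only where a 16.2.3 criterion is met, and SAP 5.6 already reports it by session.
- *That the list was chosen to suit the data.* The SAP is dated 22 July 2018, and Section 3.4 cites an observed one-subject difference between populations. The documents therefore do not show that the list came before the coded events. They do not show the reverse either.

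**Conclusion.** The point holds as an unreconciled difference in case definition for a named safety endpoint, and as an inconsistency within the SAP between 2.6.2 and 2.9.2 on one side and 5.5 on the other. The SAP explains other departures from the protocol, such as the single dose group in 2.9 and the choice of population in 3.4, but not this one.

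The size and direction of any effect on reported incidence cannot be determined. The ranges above rest wholly on assumed values of *p*, *s* and *f* and show only that either sign is possible. The conclusion assumes that 5.5 is the dental adverse event analysis announced in 2.9.2, and that no undescribed shell tabulates the eCRF designation. If such a shell exists, the remaining defect is that the SAP does not say so.

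This is more than a missing detail, because the endpoint's incidence should follow the endpoint's own definition. No hypothesis test is affected, and the individual events remain visible in the general adverse event output.

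**What to change.** In SAP 5.5:

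1. Tabulate the dental adverse event endpoint from the eCRF dental designation in Protocol 16.2.3, by session and overall, as number and proportion of subjects.
2. Keep the Table B list as a supportive analysis, labelled as such, stating who compiled it, from what source and when.
3. Cross-tabulate designation against list, and list the discordant events.
4. Record that the list-based selection departs from the protocol's case identification, and give the reason.

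The protocol already requires the designation to be recorded, so no new data are needed. The cost is SAP wording and one extra table with its cross-tabulation. Reported dental incidence may rise or fall.

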5.6 Adverse Events Associated to Distant Spread of Toxin Effect

Incidences of subjects reporting adverse events associated with distant spread of toxin effect per the Agency-provided list will be reported for each treatment session.

Table C – Listing of Distant Spread of Toxin Effect Terms used for Analysis

Term		
Accommodation disorder	Areflexia	Aspiration
Botulism	Bradycardia	Bulbar palsy
Constipation	Cranial nerve palsies multiple	Cranial nerve paralysis
Diaphragmatic paralysis	Diplopia	Dry mouth
Dysarthria	Dysphagia	Dysphonia
Dyspnoea	Extraocular muscle paresis	Eyelid function disorder
Eyelid ptosis	Facial palsy	Facial paresis
Hemiparesis	Hypoglossal nerve paresis	Hyporeflexia
Hypotonia	IIIrd nerve paresis	Ileus paralytic
IVth nerve paresis	Monoparesis	Muscular weakness
Paralysis	Paralysis flaccid	Paraparesis
Paresis	Paresis cranial nerve	Peripheral nerve palsy
Peripheral paralysis	Pelvic floor muscle weakness	Pneumonia aspiration
Pupillary reflex impaired	Quadriparesis	Respiratory arrest
Respiratory depression	Respiratory failure	Speech disorder
Trigeminal nerve paresis	Urinary retention	Vision blurred
Vocal cord paralysis	Vocal cord paresis	

Details of adverse events associated with distant spread of toxin effect will be listed for each subject.

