During the screening period, the following will be assessed to evaluate the subject's eligibility to participate in the study: inclusion and exclusion criteria; medical, surgical, and medication history; presence or prior history of aspiration, aspiration pneumonia, choking, and/or dysphagia; complete physical exam (including vital signs, height, and weight); neurologic exam; dental exam; clinical laboratory testing; urine pregnancy testing (females of childbearing potential only); and forced vital capacity (FVC) (if warranted, such as in ALS patients). All subjects successfully completing screening will have the following procedures/assessments conducted at baseline (Day 1) before the first injection of MYOBLOC: brief physical exam (including vital signs); FVC (if warranted); neurologic exam; Columbia Suicide Severity Rate Scale (C-SSRS); oral exam; saliva production quantitatively determined via USFR; qualitative assessments by the Investigator including CGI-S and DFSS-I; subject assessments including PGI-S, DFSS, DIS; and urine pregnancy test (result must be negative to proceed with the injection). Those subjects who satisfy all eligibility criteria may receive a dose of MYOBLOC (3,500 Units) via injections into the submandibular and parotid glands on Day 1. Subjects will be contacted by telephone 24 hours post-injection to inquire about their health status.

Subsequent study visits will occur at Weeks 4 (± 3 days), 8 (± 3 days), 13 (± 2 weeks), 17 (± 5 days), 26 (± 2 weeks), 30 (± 5 days), 39 (± 2 weeks), 43 (± 5 days), and 52 (± 2 weeks), with safety and effectiveness assessments made as detailed in the Schedule of Assessments in Table 2 in Section 14.1; telephone follow up will be done at Weeks 14 (± 1 day), 21 (± 5 days), 27 (± 1 day), 34 (± 5 days), 40 (± 1 day), and 47 (± 5 days)

Injections at each treatment session will be done when the subject returns to baseline status as determined by the Principal Investigator, with a minimum interval of 11 weeks from the prior injection but no later than 15 weeks from the prior injection. If after the first treatment of 3,500 Units the subject develops intolerable side effects, but still wishes to remain in the

study, the Investigator has the discretion to decrease subsequent doses, but to no less than a total dose of 2,500 Units.

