2 STUDY DESIGN

2.2 Description of Trial Design

This is a multi-center study with a single arm to evaluate the long-term safety and effectiveness of repeated doses (MYOBLOC 3,500 Units single-injection treatment) at intervals of every 13 weeks over a maximum possible duration of 1 year in subjects with troublesome sialorrhea. The study population will be comprised of a mixture of patient populations, including subjects with PD-related sialorrhea, subjects with sialorrhea secondary to other non-PD conditions (e.g., cerebral palsy, ALS, stroke, traumatic brain injury) or secondary to oral cancer or medications (e.g., neuroleptics).

After a screening period (up to 21 days), those subjects who satisfy all eligibility criteria will receive single dose injections of 3,500 Units of MYOBLOC at Day 1 and at subsequent intervals of every 13 weeks (+/-2 weeks) for a total of 4 treatments via injections into the submandibular and parotid glands. Repeat injections at each treatment session will be done when subjects return to baseline status as determined by the Investigator, with a minimum of 11 weeks from the prior injection. After the 1st treatment session for which subjects are injected

with 3,500 Units, the Investigator has the discretion to decrease subsequent injection doses, as a result of poor tolerability, but to no less than a total dose of 2,500 Units.

Subjects will undergo safety and effectiveness assessments at Day 1 (1st injection), and Weeks 4, 8, 13 (2nd injection), 17, 26 (3rd injection), 30, 39 (4th injection), 43, and 52. Telephone follow-up will occur at Weeks 14, 21, 27, 34, 40 and 47 to assess how the subject feels after 1 week (± 1 day) of study drug injection, document adverse events as appropriate, document any new medications the subject may be taking and remind the subject to complete their diary.

At each visit, the following efficacy assessments will be collected, when possible by the same assessor for a given subject:

- Unstimulated salivary flow rate (USFR)
- Clinical Global Impression of Severity (CGI-S)
- Clinical Global Impression of Change (CGI-C), except for Day 1
- Drooling Frequency and Severity Scale (DFSS-I) by Investigator
- Drooling Frequency and Severity Scale (DFSS-S) by subject
- Patient Global Impression of Severity (PGI-S)
- Patient Global Impression of Change (PGI-C), except for Day 1
- Drooling Impact Score (DIS) by Subject

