2.4 Randomization

2.4.1 Treatment randomization

This is an open-label study with a single arm, and all eligible subjects will receive the same dose of 3,500 Units of MYOBLOC. No treatment randomization is necessary.

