2.9.2 Safety analysis

Safety measures include adverse events, adverse events of special interest (AESI), dental adverse events (DAE), adverse events associated with distant spread of toxin effect, vital signs and weight, physical exam, neurological exam, dental exam, oral exam, and clinical laboratory tests, as well as lung functioning test for ALS subjects. Adverse events will be coded using the Medical Dictionary for Regulatory Activities (MedDRA) adverse event dictionary.

Like for effectiveness analyses, the baseline for safety analysis includes the pre-injection visits of Day 1, and Weeks 13, 26, and 39, respectively, for each of the treatment sessions 1 through 4.

Drug Exposure

Frequency of drug exposure will be calculated based on the number of injections of study drug administered. Duration of drug exposure will be calculated for each subject for the average duration of individual treatment sessions and total duration of treatment sessions, with the former being the average of the durations of individual treatment sessions the subject has received and the latter being the sum of the durations of individual treatment sessions the subject has received. Duration of drug exposure will be summarized for the safety population as defined in Section 3.1.

Early Termination

Subjects' study disposition will be summarized. A listing will be provided for all early terminations. This listing will include a subject's demographic variables, primary diagnosis, number of injections administered, and the primary reason for early termination.

Adverse Events, AESI, and DAE

All of adverse events will be coded for preferred terminologies using MedDRA. An AE that occurs on the 1st injection date or later will be defined as a TEAE. An AE with start date missing and no valid stop date or stop date being after the first injection date will be considered as a TEAE. TEAEs will be further separated by treatment session.

TEAEs, AESIs, DAEs, and adverse events associated with distant spread of toxin effect will be analyzed by session. Frequency of these types of adverse events will be calculated for each body system (or system organ class, SOC), by preferred term, for number of subjects and proportion reporting the event. The severity of adverse events and the relationship to study medication will be summarized for each body system and preferred term.

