5.4 Adverse Events of Special Interest (AESI)

Analyses of AESI will include aspiration, aspiration pneumonia, choking, and dysphagia. Incidences of subjects reporting AESI will be reported for each treatment session. Details of AESIs will be listed for individual subjects will be listed.

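### The planned AESI and distant-spread tables count subjects per 11-to-15-week session and ignore time since injection, so they do not separate early post-injection events from background disease events

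*SAP*

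**What the plan says.** The rule for adverse events is in SAP 2.9.2: "TEAEs, AESIs, DAEs, and adverse events associated with distant spread of toxin effect will be analyzed by session". SAP 5.4 repeats it for AESI: "Incidences of subjects reporting AESI will be reported for each treatment session". SAP 5.6 repeats it for distant spread: "Incidences of subjects reporting adverse events associated with distant spread of toxin effect per the Agency-provided list will be reported for each treatment session". The term list in that section (Table C) has 50 entries.

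Protocol 10 sets the session length, with re-injection "with a minimum interval of 11 weeks from the prior injection but no later than 15 weeks from the prior injection". It ties re-injection to recovery: "Injections at each treatment session will be done when the subject returns to baseline status as determined by the Principal Investigator". SAP 2.4.1 confirms that there is no comparator: "This is an open-label study with a single arm, and all eligible subjects will receive the same dose of 3,500 Units of MYOBLOC". SAP 2.2 describes the subjects: "The study population will be comprised of a mixture of patient populations, including subjects with PD-related sialorrhea", together with others such as ALS, stroke, traumatic brain injury and cerebral palsy.

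The plan has other material on causality:
- SAP 2.9.2 summarizes severity and relationship to study drug by body system and preferred term. SAP 5.4 and 5.6 list events by subject.
- Protocol 16.2.2.2 makes onset relative to dosing a criterion in each causality grade, and asks separately whether the event is related to the underlying disease.
- Protocol 17.7 plans TEAE incidence with disease-related events removed. The SAP text available does not include that analysis.

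**The concern.** Long-term safety is the primary objective. Dysphagia, dysarthria, muscular weakness, dyspnoea, hemiparesis and respiratory failure are all in Table C, and all can arise from the diseases enrolled. Without a control arm, a per-session incidence is background plus any drug effect.

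Time since injection is the obvious internal contrast. Events caused by toxin spread would be expected to cluster after injections, whereas events from disease progression have no reason to follow the injection calendar. SAP 2.9.1 and 2.9.2 keep the 4-, 8- and 13-week time points for effectiveness, vital signs and C-SSRS, but not for AESI or distant spread, where timing says most about cause. The information at stake is already in the onset and injection dates.

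**Working it through.** **Session length.** 13 - 2 = 11 and 13 + 2 = 15 weeks, which agrees with Protocol 10.

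**Inputs.** N = 187 is from SAP 2.5. The documents give no background rate, effect size or expected number of events, so the rest are assumptions: 13-week (91-day) sessions, constant background, any drug effect confined to the first 4 weeks (28 days), independent events and no attrition.

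**1. What the session table cannot see.** With background incidence b per session and a rate R times higher in days 1-28:
- session incidence = b × (28R + 63)/91
- share of onsets in days 1-28 = 28R/(28R + 63)

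| b | R | Session incidence | Events in 187 | Share in days 1-28 |
|---|---|---|---|---|
| 5% | 3 | 0.05 × 147/91 = 8.1% | 15.1 | 84/147 = 57% |
| 8.1% | 1 | 8.1% | 15.1 | 28/91 = 31% |

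The session table is the same in both rows. The onset distribution is not.

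**2. Size of the signal.** Let s be the fraction of events that are toxin-related.
- share in weeks 0-4 = s + (1 - s) × 4/13
- share in weeks 8-13 = (1 - s) × 5/13
- rate ratio = (first share/4) ÷ (last share/5)

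| s | Weeks 0-4 | Weeks 8-13 | Rate ratio |
|---|---|---|---|
| 0 | 0.308 | 0.385 | 1.00 |
| 0.25 | 0.481 | 0.288 | 2.08 |
| 0.50 | 0.654 | 0.192 | 4.25 |

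**3. Power for that ratio.** Condition on the events in the first and last windows. Under no effect, each falls in the first with probability 4/(4 + 5) = 4/9. Use an exact one-sided 2.5% binomial test, averaged over the number of events in the two windows.

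| Total events | Power, s = 0.25 | Power, s = 0.50 |
|---|---|---|
| 10 | 8% | 33% |
| 20 | 22% | 72% |

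Repeated events within subjects would change these figures.

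**4. Effect of imputed dates.** SAP 2.8 sets completely unknown start dates, and dates missing day and month, to the first injection. These all land in weeks 0-4. With 20 events and no toxin effect:
- 2 imputed (10%): first window 2 + 18 × 4/13 = 7.54; last window 18 × 5/13 = 6.92; ratio (7.54/4)/(6.92/5) = 1.36.
- 4 imputed (20%): first window 4 + 16 × 4/13 = 8.92; last window 16 × 5/13 = 6.15; ratio (8.92/4)/(6.15/5) = 1.81.

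**5. Session length.** The no-effect share in the first 4 weeks is 4/11 = 36% at 11 weeks and 4/15 = 27% at 15. Rates per person-week avoid dependence on an assumed length.

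**The case against.** **Attribution exists.** A reader might infer that the plan has nothing to tell toxin effects from disease. The documents do not support that. Timing enters every causality grade, disease attribution is recorded separately, AESI have written diagnostic criteria and a screening baseline (Protocol 16.2.4), and relationship summaries, listings and narratives are planned. This stands, and it limits the point to the aggregate AESI and distant-spread tables. Those attributions are still open-label judgments. Protocol 16.2.2.2 also defaults doubtful events to at least possibly related and says an event would generally not be related to both drug and disease.

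**Protocol 9.1.** Its wording, "Occurrence of adverse events of special interest (i.e., aspiration, aspiration pneumonia, choking, dysphagia) at each study visit as assessed by the Investigator", could be taken as a promise of by-visit analysis that the SAP broke. The same by-visit phrase is used for all adverse events and the C-SSRS, so it reads as a collection schedule. Protocol 17.7 itself specifies analysis by session, and the SAP follows it.

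**The late window is not a proven drug-free reference.** Return to baseline status is not defined, and Protocol 13.2 anticipates moderate to severe dysphagia or dry mouth persisting to the end of the injection window. This stands. Persisting effects matter less for onsets than for prevalence, but the low-effect window remains an assumption.

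**An onset table can mislead.** Besides imputed dates, contacts are denser early: Protocol 14.8 adds a 24-hour call in Session 1 and a one-week call in later sessions, so weeks 0-4 have two contacts and each later window has one. Dry mouth is in Table C but is a plausible local effect of injecting salivary glands, so pooling it could produce early clustering unrelated to distant spread. These points stand and shape the fix.

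**Unseen shells.** The SAP contents list table, listing and figure shells (7 to 9) that were not available. An onset table there cannot be ruled out.

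**Conclusion.** The point holds for the aggregate tables. In the SAP text available, AESI and distant-spread events are summarized only over 11-to-15-week sessions, and no summary uses time since injection. In a single-arm ALS, PD and stroke population, those tables do not separate early post-injection events from background. It does not follow that separation is impossible: it rests on open-label attribution, and the one planned analysis that would have used disease attribution, in Protocol 17.7, is not carried into that text.

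The gain from adding timing is real but modest. Under the stated assumptions, the rate ratio moves from 1.0 to 2.1 or 4.3 when a quarter or half of events are toxin-related. Twenty independent events would detect this with about 22% or 72% power, and the event count is itself an assumption. The table would therefore be supportive and descriptive, not a test of causation. It is worth adding because it is cheap and bears on the primary objective.

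**What to change.** Keep the per-session incidence. In SAP 5.4 and 5.6 add one descriptive, supportive table of AESI and distant-spread onsets by time since the most recent injection: 0-4 weeks, >4-8 weeks, and >8 weeks to the next injection or end of follow-up.

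- Give events per 100 person-weeks in each window, and the first-to-last rate ratio with a 95% CI that allows for repeated sessions per subject.
- Exclude events whose start date was imputed under SAP 2.8, or show them on a separate line.
- Present by preferred term with dry mouth separate, and by underlying diagnosis where counts allow.
- State in a footnote that early contacts are denser and that the last window is only an assumed low-effect reference.

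Also restore the Protocol 17.7 incidence without disease-related TEAEs. If the shells in SAP 7 to 9 already hold either analysis, describe it in the SAP body.

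The cost is one new table and one restored one, from data already collected. No new visits or data are needed. The remaining weaknesses are wide intervals if events are few, and onset dates partly recalled at contacts.
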